### **3.4 The Development of the Online Platform at MSKCC**

The online platform we plan to use in his study is the WEBCORE system, which is currently being used in MSKCC protocols 04-020 and 07-034 (CALGB 70501) and has previously undergone security and privacy reviews at MSKCC. The WEBCORE system was developed at MSKCC as a collaboration between study Investigators in the Departments of Medicine, Epidemiology and Biostatistics (including members of its Computing Resource group who maintain the infrastructure of the CRDB), and Information Systems. During the creation of WEBCORE, aesthetic aspects of the questionnaire and user-friendliness of the interface were improved based on feedback from the initial cohort of patients in the gynecologic oncology clinic receiving chemotherapy. Usability testing was also conducted. The technical functionality of

**Memorial Sloan-Kettering Cancer Center  
IRB Protocol**

**IRB#: 08-155A(8)**

**3.3 WEBCORE Postoperative Course following Gynecologic Surgery at MSKCC**  
By collaboration from members of the Computing Resource Group in Epidemiology and Biostatistics. Security issues are described in Section 13.2, the logistics of logging into WEBCORE in Section 4.2.3, and generation of WEBCORE Reports for clinician use in Section 4.2.4. A diagram of the system architecture/server configuration is reproduced in Appendix 7.

**3.5 Preliminary PRO Research at MSKCC**

[name] MD, a Co-Investigator for this protocol, conducted a feasibility study in 110 patients with gynecologic malignancies receiving chemotherapy to evaluate patients' ability and willingness to self-report toxicity-related symptoms of chemotherapy toxicity online or on clinic portals [13]. The WEBCORE secure web-based PRO platform was used for this study [10]. During an 8-week observation period, 80% of patients used the system to self-report without prompting. Most patients (96%) found WEBCORE easy to use, and 98% would recommend it to others. In addition, clinicians responded to WEBCORE-generated alerts for potentially concerning symptoms: there were 42 automated email alerts sent to clinicians due to grade 3 or 4 chemotherapy toxicities triggered by 16 different patients from home computers. These alerts prompted seven telephone contacts, three medication changes, and three new scheduled appointments.

A follow-up study in 100 patients with lung cancer receiving chemotherapy yielded similar results [7, 10], demonstrating that WEBCORE has been pilot tested for general feasibility and acceptability. [name] is currently conducting a randomized controlled trial to determine if patient self-reporting of symptoms during chemotherapy impacts on efficiency or clinical outcomes, as well as a multi-center feasibility study of PROs in the CALGB.

While electronic capture of PROs has been shown to be longitudinally feasible in patients treated nonsurgically for gynecologic cancer [13, 28], this group is different than women undergoing extensive surgery, who experience significant short-term disability during recovery. The ability and willingness of gynecologic cancer patients to electronically report post-operative outcomes has not been assessed. Symptom and HRQL information elicited via these methods could potentially improve outcomes and detect complications earlier.

**3.6 Computer and Internet Use Among MSKCC Patients**

Implementation and evaluation of an Internet-based tool for patients depends on the ability of patients to access and use a computer/the Internet. In order to characterize Internet use by MSKCC patients and their companions, [name] and [name] conducted an anonymous waiting-room survey of patients presenting to the general surgical and medical oncology outpatient departments between December 1999 and February 2000 [29]. Of the 625 individuals approached, 443 completed and returned questionnaires (223 patients and 220 companions). The mean age of patients

**Memorial Sloan-Kettering Cancer Center  
IRB Protocol**

**IRB#: 08-155A(8)**

diagnosis (45%), followed by pancreatic/biliary (8%), gastro-esophageal (8%), hepatic (6%), sarcoma (5%), and endocrine (5%). Among the respondents, 64% of patients and 76% of companions owned computers, and Internet access was available at home to 58% and 68% respectively (Table 1).

**Table 1: MSKCC Survey Results (12/99 – 2/00)**

Cancer patients with home computers	64%
Companions of cancer patients with home computers	76%
Cancer patients with home Internet access	58%
Companions of cancer patients with home Internet access	68%

In November-December 2003, [name] conducted an informal anonymous survey of 90 patients (30 with gynecologic malignancies, 30 with lung cancer, 30 with prostate cancer) in waiting-areas of the MSKCC outpatient clinics (Table 2). Ages ranged from 40 to 84. The majority of patients noted regular access to the Internet. All patients without regular access to a computer or the Internet were older than 75 years, whereas all patients younger than 75 years had regular access. Of the patients who used the Internet, one patient used the Internet at a library, all others at home. All patients with home access expressed interest in electronic symptom self-tracking. When shown a demonstration of WEBCORE (the version used for tracking chemotherapy toxicity), all patients with Internet experience stated they would be interested in regularly using WEBCORE.

**Table 2: Informal MSKCC Survey of 90 Outpatients Receiving Chemotherapy (11-12/03)**

	GYN	LUNG	PROSTATE
Do you have regular access to a computer (home, library, other)?	83%	68%	83%
Do you use the Internet regularly? (If not, is there somebody at home who does?)	73% (50%)	65% (56%)	70% (60%)
Do you use email?	60%	48%	64%
Would you be interested in regularly using WEBCORE to enter symptom information into an electronic diary over the Internet?	80%	70%	88%

## Memorial Sloan-Kettering Cancer Center IRB Protocol

**IRB#: 08-155A(8)**

As of October 2007, 79% of U.S. adults are online, and of those, 72% access the internet from home. Use is generally greatest among individuals who are younger, more affluent, better-educated, and white, although use is increasing among those over 50 years-old and with incomes below \$25,000 [30].

A 2006 study by the Pew Research Center found that 80 percent of internet users, or 113 million U.S. adults, seek health information online, and that women are more likely to do so than men [31]. Surveys suggest significant numbers of patients want to communicate with physicians over the Internet [32, 33]. Many patients consider use of the Internet to enhance the patient-physician relationship [34, 35]. Most U.S. physicians regularly access the Internet and use daily email, and an increasing number communicate with patients via email [36-41]. Preliminary research suggests that online access to patient records and secure online communication with health providers may decrease the amount of patient follow up visits among chronically ill patients [42], leaving more time for new patient visits, or patients with more pressing concerns.

Despite a large number of informational web sites available for cancer patients [43], there is little opportunity for patients to use electronic resources to record their symptoms or communicate with clinicians. For cancer patients receiving routine outpatient care, the development of resources such as WEBCORE may allow for linking to more appropriate informational services, may foster better discussions with clinicians, save time, and inform better treatment decisions.

### 3.7 Future Directions

If this preliminary work finds the PRO approach to data collection to be feasible in the post-operative setting, it could lay the groundwork for: 1) further evaluations of feasibility in other populations (ie, underserved, non-English speaking); 2) a randomized trial to determine if patient self-reporting in the post-operative setting improves clinical outcomes (complication rates/morbidity, satisfaction with care, etc); and 3) assessments of this data collection method in the multi-center clinical trial setting (eg, nested in a GOG or CALGB treatment trial). In addition, follow-up work would be merited to refine the questionnaire items and electronic platform, and to devise backup data collection methods for patients who are unable or unwilling to complete electronic questionnaires.

## 4.0 OVERVIEW OF STUDY DESIGN/INTERVENTION

### 4.1 Design

This pilot study will assess patient use of WEBCORE, an online system designed for cancer patients to self-record toxicity-related symptoms based on NCI Common Terminology Criteria for Adverse Events and global quality of life (QoL) by European Organization for Research and Treatment of Cancer (EORTC QLQ-C30).

The overall objective of this study is to assess if online self-reporting of symptoms in

**Memorial Sloan-Kettering Cancer Center  
IRB Protocol**

**IRB#: 08-155A(8)**

the post-operative period is feasible and well-accepted by patients and clinicians. This is a single-arm pilot study in which patients with gynecologic malignancies will self-report their own symptoms and HRQL during the post-operative period using the online platform WEBCORE.

Eighty patients with home internet access and regular email use undergoing laparotomy for presumed or confirmed gynecologic cancer will be recruited from MSKCC outpatient clinics. Enrollees will be sent weekly email reminders to login to WEBCORE from home (Appendix 10). Participants will be expected to complete the questionnaire once pre-operatively and then weekly starting 7 days after surgery until the 6-week post-operative period has ended. Entered information will be stored in a secure database located on a firewall-protected MSKCC server. If an enrolled patient fails to login and self-report within 24 hours of the automated reminder, a second reminder email will be sent. If the patient again fails to respond, a backup telephone call to the patient will be made by the clinical research fellow coordinating this study. The back-up phone call will be made within a week of the initial missed questionnaire. If the patient is unreachable, a total of 3 attempts will be made to reach the patient. The fellow will use a semi-scripted approach to complete the symptom questionnaire, and to ascertain reasons for non-completion of the online survey.

A WEBCORE report summarizing patient symptom trends will be printed and made available to the clinician at the time of the post-operative visit. Additionally, if a patient submits a response that is concerning according to pre-specified limits set by the gynecologic oncology service, an automated email alert flagged as “urgent” and titled “severe Patient-reported symptom” will be sent in real-time to the research fellow, the designated RSA and the PI of the study. The research fellow will forward the email to the POA of the patient’s gynecologic oncologist and to the clinic nurse taking patient calls for that gynecologic oncologist that day. (This is the same system used presently to triage patient phone calls.) If the research fellow is not available, coverage will be provided by the designated RSA. In that event, the designated RSA will notify the POA of the patient’s gynecologic oncologist and the clinic nurse taking patient calls for that gynecologic oncologist that day. No specific responses to these emails will be required, but any actions taken in response to these alerts by clinicians will be tracked (ie, telephone calls, supportive medication prescriptions, new appointments made, etc) using a form emailed to the nurse after the automated email alert (Appendix 5) and the “Ambulatory Care Phone/Email Communication Form” in the EMR. The forms will be collected by the research fellow or by the designated RSA.

It will be emphasized to patients that there is no regular monitoring of information entered into WEBCORE. In addition, anytime a patient enters a potentially concerning response into WEBCORE, a popup box will appear on the screen reminding her to consider calling her physician.

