**IRB#: 08-155A(8)**

**1.0 PROTOCOL SUMMARY**

**1.1 Background**

There is a paucity of research on health-related quality of life (HRQL) in patients with gynecologic cancer in the 6-week period after major cancer surgery. Publications from other surgical disciplines have found that physicians tend to underestimate patient symptoms [1, 2]. The NIH, the FDA, and other regulatory agencies [3-5] have recognized patient-reported outcomes (PROs) as important in evaluating disease and treatment. Reducing the burden of treatment-related symptoms, especially during aggressive therapy, is an important cancer care goal. Gynecologic cancer surgery is associated with multiple moderate to severe symptoms and potential severe surgical complications, especially during the first postoperative month. Effective symptom control is depending on timely symptom assessment and sufficient feedback from patients to practitioners so that adjustment in symptom control can be initiated. Patients are often reluctant to report symptoms, enduring high levels of symptoms. The main purpose of this pilot study is to clarify whether patients are willing to self-report common toxicity information and quality of life using the WEBCORE system via the Internet. Web-based patient self-reporting from home between clinic visits could potentially improve the quality of post-operative care through earlier detection of symptoms; improve patient-doctor communication; and provide an efficient means for data capture in clinical trials evaluating the effects of surgical interventions on patient safety and HRQL [6]. However, it is not known as to whether patients will be able or willing to self-report symptoms during this period, or if clinicians will find this information to be clinically useful. If WEBCORE is utilized and patient feedback is generally positive, future investigation will be considered reasonable in order to assess the potential value of WEBCORE in postoperative care of cancer patients and in the setting of clinical treatment trials.

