According to the 2006 FDA Draft Guidance on the use of PROs in clinical research, "a PRO is any report that comes directly from a patient about a health condition or its treatment without interpretation of the patient's response by a clinician or anyone else" [3,5]. As a result of this guidance, increasing emphasis has been placed on the appropriate use of PROs in clinical trials for detecting potentially concerning adverse effects and complications of cancer and its treatments. The NIH has sponsored a national initiative (PROMIS), a key project of the Roadmap Initiative, with an overarching goal to improve assessment methods of self-reported symptoms and HRQL outcomes in chronic diseases including cancer [4]. Included in that project is the development of a national databank of PRO items and instruments. The NCI and the American Cancer Society have both prioritized the integration of PROs into clinical practice and research, as demonstrated by the joint NCI-ACS-FDA hosting of the Patient Reported Outcomes in Cancer Trials (PROACT) conference in September of 2006. The conference sought to identify circumstances in which PROs are indicated, best practices for their use, and to establish a platform from which PROs can be efficiently incorporated into NCI clinical trails [18].

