**4.2.1 The Online Platform**

This design consists of a homepage for patients to login to WEBCORE, followed by screens containing a single question on each page. This design was refined through usability testing at MSKCC.

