## **9.0 PRIMARY AND SECONDARY OUTCOMES**

### **9.1 Primary Outcome**

The primary objective of this study is to evaluate the feasibility of patients using WEBCORE to track their own symptoms and HRQL while recovering from laparotomy for presumed or confirmed gynecologic cancer. In this pilot feasibility study, we will measure several parameters related to patients' utilization of the WEBCORE system, in order to evaluate the potential for implementation of collecting patient self-reported measures in a gynecologic oncology practice and/or in clinical trials.

- To gauge patients' willingness to record their experiences we will record the ratio of the number of patients approached for study participation to the number who enroll. The proportion of patients approached versus consented will be tracked continuously by the Research Fellow and the designated Surgery RSA.
- We will evaluate the extent to which patients who enroll in the protocol use the WEBCORE system to self-report symptoms and HRQL. Specifically, we will measure how often each user accesses the WEBCORE system, and will note the time and date that utilization occurs. Perfect compliance would be logging on and completing all the questions seven times: once pre-operatively, and then weekly for six weeks following surgery. In keeping with standards for the assessment of feasibility of online platforms, as a crude measure of feasibility, we will consider the study results to suggest that WEBCORE is a strategy warranting larger scale evaluation if approximately 80% of participants login to WEBCORE at least four times during the study period [13]. In our analysis, we will look at WEBCORE utilization (1) over time and (2) in relation to the presence or absence of documented minor and major surgical complications. The proportion of users who logged in with or without a follow-up reminder email will be tabulated. We will assess for attrition of compliance over time by measuring the proportion of patients who login during each consecutive week of observation.
- Results of backup telephone calls made when patients have not logged in will be tabulated to assess if the reported symptoms of such patients differ from reports of patients who have logged in on time, and reasons for non-compliance.

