**IRB#: 08-155A(8)**

**11.2 Primary Objective**

The primary objective of this study is to evaluate the feasibility of patients using WEBCORE to track their own symptoms and HRQL while recovering from laparotomy for presumed or confirmed gynecologic cancer. We will calculate summary statistics for several measures of utilization, including the frequency with which each user logs in and completes a WEBCORE online questionnaire; the proportion of patients who log in at each sequential week of follow-up; and when utilization occurs in relation to surgery and/or complications. If at the end of the study 58/79 are responders (a responder is a person who has logged in at least 4/7 times and completed at least half of the questions each time) then we will conclude that the use of WEBCORE in this population is feasible. If this hypothesis is true, we will consider the study results to suggest that WEBCORE is a strategy warranting larger scale evaluation [13]. Baseline patient characteristics and disease information will be examined via a logistic regression for their relationship to a patient's likelihood of being a responder. The following predictors will be considered: type of cancer, type of surgery, stage of disease, computer experience/age/education

In our analysis, we will look at WEBCORE utilization (1) over time and (2) in relation to the presence or absence of documented minor and major surgical complications. We will tabulate the proportion of users who logged in with or without a follow-up reminder email. We will assess for attrition of compliance over time by measuring the proportion of patients who login during each consecutive week of observation. Results of backup telephone calls made when patients have not logged in will be tabulated to assess if the reported symptoms of such patients differ from reports of patients who have logged in on time, and reasons for non-compliance. We will calculate the proportion of WEBCORE responders compared to the total number of enrollees (responders: enrollees), as well as the proportion of responders compared to total number of patients eligible (responders: eligible). Baseline characteristics for those who refuse enrollment will be compared to those who agree to participate.

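### Missed-login symptoms come from a semi-scripted telephone call and on-time symptoms from online self-report, so the planned comparison cannot separate non-login from mode and interviewer wording

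*Combined protocol and SAP*

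**What the plan says.** Section 4.1 (Design) sets out what happens after a missed form. A second email follows if there is no login within 24 hours of the first reminder. If that also fails, "a backup telephone call to the patient will be made by the clinical research fellow coordinating this study", within a week of the missed form and with up to three attempts. On the content of the call: "The fellow will use a semi-scripted approach to complete the symptom questionnaire, and to ascertain reasons for non-completion of the online survey". Section 4.2.3 describes the same call more briefly, as administering the questionnaire and finding out why it was missed.

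Patients who log in answer by themselves. Section 4.2.1 (The Online Platform) describes a login page "followed by screens containing a single question on each page".

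Section 9.1 says the call results will be "tabulated to assess if the reported symptoms of such patients differ from reports of patients who have logged in on time", and Section 11.2 repeats this. Section 11.3 gives the purpose: patients may skip the form because they feel well or because they are too ill, and the call is meant to help tell these apart. The same section expects less use by patients with the worst symptoms.

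**The concern.** The comparison is meant to show whether patients who miss a form are more or less symptomatic than those who complete it. Their answers are collected in a different way: by voice, with a member of the study team asking, in wording that is only partly fixed. If the way of asking shifts the answers, the table will show a difference where there is none, or hide one that exists.

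The protocol itself treats the route of a report as important. Section 3.1 cites the definition that "a PRO is any report that comes directly from a patient about a health condition or its treatment", and the definition goes on to exclude interpretation of the answer by a clinician or anyone else. Section 7.3.1 keeps a poorly fitting EORTC item rather than alter a validated instrument. Leaving the wording of the symptom items open on the telephone is out of keeping with that care.

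What is at stake is the reading of why forms were missed, and hence whether the online symptom data under-represent the sickest or the best-recovered patients.

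**Working it through.** The plan states no sample size, effect size or precision for this comparison, so there is no figure to reproduce. The check is whether the table can separate the two effects.

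**1. Mode by login status.**

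| Report | Source in plan | Mode | Who words the question |
|---|---|---|---|
| Logged in on time | 4.2.1 (The Online Platform), 4.2.3 | Online, self-completed | Fixed screen text |
| Missed after second reminder | 4.1, 4.2.3 | Telephone | Fellow, semi-scripted |

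The other two combinations, an on-time report by telephone and a missed-login report collected online, do not occur in this comparison. Mode and login status coincide completely. A form completed online after the second reminder is online but not clearly on time, and the plan does not say where it is counted.

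**2. What the table estimates.** For any symptom, let Δ be the true difference (missed minus on-time) in the share reporting it as severe. Let m be the change caused by telephone interview rather than online self-report. The tabulated difference is

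D = Δ + m.

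Each item gives one observed D and leaves two unknowns.

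**3. Illustration.** The documents give no value for m. Assume it lies between -10 and +10 percentage points.

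- True Δ = 0: D runs from 0 - 10 = -10 to 0 + 10 = +10.
- True Δ = +10: D runs from 10 - 10 = 0 to 10 + 10 = +20.

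An observed D of zero to +10 is therefore compatible with either truth.

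**4. Does another section deal with it?** Section 11.2 tabulates without any mention of mode. Section 11.3 describes the purpose of the call but not its wording. Section 11.5 covers skipped items and incomplete forms only. The appendix list in Section 17.0 contains no call script.

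**5. Could a within-patient comparison isolate m?** A missed form does not make a patient a permanent non-user, so some patients will have both telephone and online reports. Their contrast is

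D(within) = m + (symptoms in missed weeks - symptoms in login weeks).

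A patient is telephoned only in weeks she missed, possibly because she was unusually ill or unusually well. Adjusting for post-operative week does not remove that second term. The contrast describes the data and does not estimate m.

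**6. Where the result is used.** Under Sections 11.1 and 11.2 a responder is defined by logins and by questions completed at those logins. Telephone reports do not enter the count, so the 58/79 rule is unaffected.

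**The case against.** The strongest reply has three parts.

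*The direction of bias is not shown.* Section 1.1 says "physicians tend to underestimate patient symptoms" and "Patients are often reluctant to report symptoms, enduring high levels of symptoms", and a reader might infer that telephone reports will run low and so hide the sickest non-users. The documents do not support this. The first statement concerns physicians' own ratings set against patients' ratings (Section 3.2 gives the urology examples). On the backup call the patient still answers and the fellow asks and records. The second is a general remark about reluctance to report; Section 3.3 describes usual care, where the patient must decide to call, whereas here she is asked directly. This objection stands. The comparison is confounded whichever way m runs, but no direction should be claimed.

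*The table is not the only evidence.* A reader might infer that the plan could wrongly conclude that missing reports are harmless. No test, imputation or decision rule hangs on this table. Other planned sources bear on the same question: reasons given on the call, the exit survey (Section 11.3), and utilization against documented complications (Sections 9.1 and 11.2), with complication details taken from the medical record (Section 7.2). This also stands, and it limits the importance of the point.

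*It is the same questionnaire, and semi-scripted may describe the call as a whole.* This is partly right. Section 4.2.3 supports reading it as one questionnaire in two modes, so calling them different instruments would go too far. But Section 4.1 applies the semi-scripted approach to completing the symptom questionnaire as well as to the reasons, and nothing requires the items to be read as written.

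**Conclusion.** The point holds in a limited form. In the tabulation planned in Sections 9.1 and 11.2, login status and reporting mode are fully aligned, so a difference cannot be assigned to non-login alone. Neither the direction nor the size of the mode effect can be derived from the documents; the 10-point range above is an assumption that shows only how the two effects add.

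The consequence is confined to a descriptive secondary table in a single-arm pilot. The feasibility conclusion does not depend on it. The change is worth making because it costs almost nothing and removes one avoidable source of non-comparability, the interviewer's wording.

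Two sources would remain after the change. One is the difference between speaking to a person and answering on a screen. The other is the delay of up to a week before the call, during a period in which Section 4.1.3 expects scores to improve by its end.

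**What to change.** - **Section 4.1:** require the caller to read the WEBCORE symptom items and response options word for word and to record the option the patient chooses. Keep the semi-scripted approach for reasons for non-completion only.
- **Sections 9.1 and 11.2:** flag each report by mode, and state that the telephone/online difference cannot be attributed to non-use alone.
- **Optional:** a within-patient telephone/online table by post-operative week, labelled as description and not as an estimate of the mode effect.

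The cost is a line in the call instructions, one data flag and a sentence of interpretation, with no new calls, visits or patients. The downsides are a less conversational call and a slightly weaker statement about non-users. The wording has to be fixed before calls are made, since it cannot be recovered afterwards; for calls already completed, the flag and the stated limitation still apply.
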